12 SUBJECT CONFIDENTIALITY16

13 PUBLICATION POLICY17

REFERENCES.....18

Protocol Summary

Title	A Single-Center 2-Arm Study of the Enlighten and Excel V Laser for Lentiginos on the Hands
Objective	
To evaluate the effectiveness and safety in a clinic setting of two laser systems for improvement of lentiginos on the hands:
 
 1. Cutera Enlighten [REDACTED] 2. Cutera Excel V [REDACTED]
Study Design	A single-center prospective, open-label, 2-armed uncontrolled study.
Enrollment	Up to 12 subjects in each arm
Primary Endpoint	
 • Reduction of the number of lentiginos at 4 weeks [REDACTED] post-final treatment [REDACTED]
Secondary Endpoints	
 • Degree of improvement in [REDACTED] skin texture, and overall appearance of the hands at 4 weeks [REDACTED] post-final treatment. • Subject satisfaction at 4 weeks [REDACTED] post-final treatment. • Incidence and severity of adverse effects during the study period [REDACTED]
Subject Population	Female or male subjects, age 30 to 90 years, Fitzpatrick skin types I-III
Planned Schedule	
First subject enrolled: April 2016
 
Last subject last visit: June 2016 (Enlighten cohort)
 
October 2016 (Excel V cohort)

1 BACKGROUND INFORMATION

Non-invasive treatment options are in high demand by patients wanting to improve the appearance of their skin without surgical intervention. As a result, patients now have a variety of options for non-invasive skin treatments, from laser and light-based treatments to devices that utilize ultrasound and radiofrequency, however this was not always the case. Initial skin improvement procedures utilized ablative lasers, such as the carbon dioxide (CO₂) and erbium:yttrium-aluminum-garnet (Er:YAG), and resulted in substantial improvement in skin appearance, texture, rhytides and laxity[1-3]. However, since ablative treatments destroy the epidermal layer of the skin in order to penetrate and heat the deeper dermal layers, ample post-procedure recovery time is required and patients may experience side effects lasting for a few weeks. Furthermore, hypo- or hyperpigmentation, prolonged wound healing and even scarring can occur following ablative procedures [4-6]. Treatment methods with less risk of side effects and post-treatment down time are in high demand. As such, the choices are vast and varied, ranging from fractional non-ablative laser devices to those that use radiofrequency [7-15]. Fractional lasers inflict microscopic zones of thermal damage in the dermal layers of the skin without destruction of the epidermis, thereby reducing recovery time significantly as compared to ablative procedures[16]. Treatment with non-fractional, non-ablative laser devices requires little to no post-procedure recovery time. Nonablative lasers of various wavelengths are effective for improvement of skin appearance based on the principle of selective photothermolysis, whereby laser light is absorbed by hemoglobin in blood vessels and melanin in pigment-producing skin cells [17, 18]. Absorption of laser light by these molecular chromophores results in the production of heat, leading to destruction of unwanted blood vessels and pigment cells. Heat production within the dermis by the laser light also results in immediate collagen contraction and heat-induced wound healing that, over time, causes a cascade of cellular events leading to new collagen production and improved skin appearance [8, 10, 19-23].

[REDACTED]

[REDACTED]

[REDACTED]

[REDACTED]

2 STUDY PURPOSE AND OBJECTIVES

The purpose of this study is to evaluate the effectiveness and safety in a clinic setting of two laser systems for the treatment of lentigines (liver spots, age spots, or dark sun spots) on the hands:

- Cutera Enlighten dual wavelength 532 nm [REDACTED] and/or 1064 nm Nd: YAG picosecond pulse duration laser
- Cutera Excel V dual wavelength 532nm [REDACTED] long pulsed laser and/or 1064 nm Nd: YAG

The objectives of this study are to:

- 1) Evaluate the reduction of the number of lentigines on the hands, the improvement of [REDACTED] skin texture, and overall appearance, and customer satisfaction 4 weeks following treatment with one of the two study lasers.
- 2) Evaluate the rate of adverse events experienced by the study subjects.

3 STUDY DESIGN

This is a single-center prospective, 2-armed, open-label, uncontrolled study in up to 24 male or female subjects per arm, age 30 to 90 years who desire non-ablative laser treatment for treatment of lentigines of the hand, and additionally to evaluate the improvement of skin texture, and overall appearance of the skin.

Subjects will be assigned to a treatment arm using a random number generator.

[REDACTED]

Subjects will be instructed to maintain the same skin care regimen as before enrollment in the study, use daily sunscreen on the hands of SPF 50 or higher as approved by the study doctor and practice strict, diligent prevention of sun exposure.

3.1 Study Endpoints

3.1.1 Primary Endpoint

- Percent reduction in the number of hand lentigines at 4 weeks [REDACTED] post-final treatment as assessed by [REDACTED] physician.

3.1.2 Secondary Endpoints

- Degree of improvement in skin texture of the hands at 4 weeks [REDACTED] post-final treatment as assessed by a [REDACTED] physician using the Physician’s Global Assessment scale.
- Degree of improvement in overall appearance of the hands at 4 weeks [REDACTED] post-final treatment as assessed by a [REDACTED] physician using the Physician’s Global Assessment scale.
- Subject satisfaction at 4 weeks [REDACTED] post-final treatment.
- Incidence and severity of adverse device effects during the study period

3.2 Study Duration

[REDACTED]
[REDACTED]
[REDACTED]

[REDACTED]
[REDACTED]
[REDACTED].

The screening and first laser treatment may be combined into one visit provided that the informed consent process has been completed (see Section 12.2) and the subject has signed the IRB-approved Informed Consent Form prior to the commencement of any study-related procedures and device treatments.

3.3 Study Assessments

3.3.1 Percent Reduction in the Number of Lentigines

[REDACTED] physician at the study site will be asked to perform an assessment of baseline and 4 weeks post-treatment subject photographs. [REDACTED]

[REDACTED]
[REDACTED]
[REDACTED]
[REDACTED]
[REDACTED]
[REDACTED]

3.3.2 Physician’s Global Assessment Scale

At 4 weeks post-final treatment, the [REDACTED] investigator will be asked to rate the degree of improvement observed in the skin with regards to skin texture, and overall appearance. Each of the 2 improvement categories will be assessed using the Physician’s Global Assessment Scale:

- 4 = Very Significant Improvement [REDACTED]
- 3 = Significant Improvement [REDACTED]
- 2 = Moderate Improvement [REDACTED]

1 = Mild Improvement [REDACTED]
0 = No Change [REDACTED]

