3.4 Photographs

Standardized digital photographs will be taken of each subject’s hand(s) at baseline, prior to all laser treatments, immediately after each laser treatment, and at the end of study visit. [REDACTED]

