5.3 Final Follow-Up Visit

The follow-up visit will occur at approximately 4 weeks [REDACTED].

The following procedures will be performed at the follow-up visit:

1. Assessment of concomitant medications: Assess and record any additions, changes and/or deletions in prescription and nonprescription concomitant medications since the previous study visit.
2. Assess for any new procedure related adverse effects or changes to previously recorded adverse effects.
3. Digital photographs of the treated area(s) will be taken.
4. [REDACTED] Physician's Global Assessment of Improvement
5. Subject will be asked to complete and return the Subject Questionnaire.

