9.2 Data Analysis

Descriptive statistics and 95% confidence intervals and will be calculated for percent reduction in the number of hand lentigines, at 4 weeks [REDACTED]

Descriptive statistics and 95% confidence intervals and will be calculated separately for improvement in skin texture, and overall appearance of the hands, based on the Physician's Global Improvement Assessment evaluation, and also for the Subject Satisfaction Scale evaluations.

Safety measures include the incidence of treatment-related AEs, the proportion of subjects who prematurely terminate from the study due to a treatment-related AE [REDACTED]

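### The visible Physician's Global Assessment scale stops at no change; if the unredacted scale also has no level for worsening, two secondary endpoints cannot record it (a minor, conditional point)

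*Combined protocol and SAP*

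**What the plan says.** Section 3.3.2 (Physician's Global Assessment Scale) has the investigator, at 4 weeks after the final treatment, "rate the degree of improvement observed in the skin with regards to skin texture, and overall appearance". Five numbered levels are visible: four grades of improvement (4 to 1) and 0 for no change. One redaction follows each label. No visible text says how to score a subject who is worse.

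Section 3.1.2 makes both ratings secondary endpoints: "Degree of improvement in skin texture of the hands at 4 weeks" and "Degree of improvement in overall appearance of the hands at 4 weeks".

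Section 9.2 (Data Analysis) says that descriptive statistics with 95% confidence intervals "will be calculated separately for improvement in skin texture, and overall appearance of the hands". It shows no hypothesis test and no comparison between arms for these scores.

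Three other provisions bear on the point:
- Section 5.3, at the same follow-up visit: "Assess for any new procedure related adverse effects or changes to previously recorded adverse effects".
- Section 9.2, on safety: "Safety measures include the incidence of treatment-related AEs".
- Section 3.4: photographs are taken of each subject's "hand(s) at baseline, prior to all laser treatments, immediately after each laser treatment, and at the end of study visit".

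On arm size, the Protocol Summary gives "Up to 12 subjects in each arm", while Sections 3 and 9.1 give up to 24 per arm. That discrepancy is a separate matter. Both sizes are used below.

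**The concern.** A rating of change against baseline can go either way. If the lowest score is no change, the rater has nowhere to put a subject whose hands look or feel worse, and that subject is recorded as unchanged. Three things follow:

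- The scores cannot separate worse from unchanged, and no analysis of the scores can recover the difference.
- The arm mean cannot fall below 0, and it is too high whenever anyone worsens.
- The study is open-label and uncontrolled, so readers are likely to judge each arm's score against 0, which is where the scale stops.

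At stake is whether the texture and appearance results can show an unfavourable outcome at all. The primary endpoint, percent reduction in lentigines, is not involved.

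**Working it through.** The plan states no figure to reproduce. It gives no worsening rate, standard deviation (SD) or expected score for this scale, and Section 9.1 rests the sample size on clinical judgment. The check is therefore a reading of the scale followed by arithmetic on the consequence.

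**Step 1: the scale.** The visible levels are 4, 3, 2, 1 and 0. Four mean improvement, one means no change, none means worsening. The hidden text after 0 could do one of three things:
- Describe no change. Worse and unchanged then share the score 0.
- Widen 0 to mean no change or worse. They still share the score 0.
- Introduce a further, lower level. The point then falls away.

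The same single redaction follows all five labels. That fits a definition of each level better than a hidden sixth level, but it is inference and not proof.

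**Step 2: shift in the mean.** Assume one rating per subject per category. If k of n subjects are worse by one grade and are scored 0 instead of -1, the arm mean rises by k/n.

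| k worse by one grade | n = 12 | n = 24 |
|---|---|---|
| 1 | 0.083 | 0.042 |
| 2 | 0.167 | 0.083 |
| 3 | 0.250 | 0.125 |

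**Step 3: shift against the precision of the mean.** The 95% confidence interval half-width is t(0.975, n-1) × SD/√n. With an assumed SD of 1:
- n = 12: 2.201/√12 = 0.635. One worse subject shifts the mean by 0.083/0.635 = 13% of the half-width.
- n = 24: 2.069/√24 = 0.422. The shift is 0.042/0.422 = 10% of the half-width.

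**Step 4: other summaries.** The proportion scoring 1 or more does not change, because a worse subject is not improved on either version of the scale. The median changes only if k is at least n/2. At an assumed worsening rate of 20%, the binomial probability of that is 1.9% for n = 12 and 0.1% for n = 24.

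**Step 5: dependence on the typical score.** Take each rating as a normal value rounded to the nearest grade, with an assumed SD of 0.75 to 1.

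| True mean | Floor at 0 raises the mean by | Cap at 4 lowers the mean by |
|---|---|---|
| 1 | 0.023 to 0.073 | at most 0.0002 |
| 2 | 0.0004 to 0.0064 | 0.0004 to 0.0064 |
| 3 | at most 0.0002 | 0.023 to 0.073 |

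The floor matters most when average improvement is small. When improvement is large, the cap outweighs it.

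**Step 6: what a worsening level would show.** Two-sided exact (Clopper-Pearson) 95% intervals for the proportion rated worse:
- 0 worse: the upper limit is 1 - 0.025^(1/n), which is 26.5% for n = 12 and 14.2% for n = 24.
- 1 worse: 0.2% to 38.5% for n = 12, and 0.1% to 21.1% for n = 24.

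**The case against.** The strongest objection is that the gap sits exactly where the text is redacted, and what is redacted cannot be called missing. A reader might infer that the plan has no worsening level. The documents do not support that, and the point is conditional for this reason.

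Second, the stated construct is improvement, which a one-sided scale measures, and harm has its own route through adverse effects. This stands in part. Section 5.3 concerns procedure-related effects, and the visible safety measures in Section 9.2 concern treatment-related events. Slightly worse texture or appearance that is not recorded as such an event would appear only as a 0. Photographs would allow a later re-rating, but no visible text plans one for these two categories.

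Third, the effect is small, and the visible analysis is descriptive. This stands, and it sets the weight of the point.

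A reader might also infer that the floor could make a laser with no net effect look beneficial. Suppose 20% worsen by one grade, 20% improve by one grade and the rest are unchanged, so that the true mean change is 0. With 24 per arm, a 95% interval for the mean would lie wholly above 0 with probability 0.736 without a -1 level, against 0.023 with one. With 12 per arm the figures are 0.205 and 0.026. The documents give no worsening rate, no reason to expect zero net change, and no test of the mean against 0. This shows sensitivity to an extreme case and is not a forecast.

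Finally, a reader might fault Section 9.2 for not asking for the frequency of each level. Descriptive statistics for a five-level score can already include those counts, so this is not part of the point.

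**Conclusion.** The point holds conditionally and is minor. The visible scale has no level below no change. If the unredacted scale has none either, a worse subject shares the score 0 with an unchanged one, the two secondary endpoints cannot show worsening, and the arm mean is biased upward whenever any subject worsens. If nobody worsens, the mean is not affected. The upward bias is measured against a scale that records the worsening; at high average scores the cap at 4 pulls the other way.

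The size is 0.083 points (n = 12) or 0.042 points (n = 24) per subject worse by one grade, about a tenth of the interval half-width under an assumed SD of 1. The proportion improved and the primary endpoint are unaffected, and the median rarely moves. The k/n figures assume one rating per subject per category and one grade of worsening. The remaining modelled figures also rest on the assumed SDs and worsening rate stated with them. The reason to act is that two endpoints would otherwise be unable to show an unfavourable result, and the remedy costs very little.

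**What to change.** 1. Check the unredacted scale in Section 3.3.2. If it already has a separate level for worsening, no change is needed.
2. If it does not, or if 0 is defined to include worsening, add one level (for example -1 = Worse) for both skin texture and overall appearance.
3. In that case, add a sentence to Section 9.2: the proportion rated worse is reported by arm for each category, with an exact 95% confidence interval.

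Reporting the frequency of every level when the scale already separates worse from unchanged is optional.

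The cost is one extra tick-box per category on the case report form and one sentence in Section 9.2. The downside is slightly less comparability with past use of the 0 to 4 scale. Recoding -1 to 0 recovers it.

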3.3.3 Subject Assessments

3.3.4 *At 4 weeks post-final treatment, subjects will be asked to complete a questionnaire to rate their level of satisfaction with the laser treatment outcome and the overall laser treatment procedure* [REDACTED]

3.4 Photographs

Standardized digital photographs will be taken of each subject’s hand(s) at baseline, prior to all laser treatments, immediately after each laser treatment, and at the end of study visit. [REDACTED]

3.5 Study Discontinuation

The sponsor (Cutera, Inc.) has the right to terminate this study at any time. Reasons for terminating the study may include, but are not limited to, the following: incidence or severity of adverse events in this or other studies indicates a potential health hazard to subjects; subject enrollment is unsatisfactory; number of protocol deviations is unacceptable; data recording is inaccurate or incomplete; or questionable study site compliance with ICH-E6, Good Clinical Practice.

3.6 Investigator Selection

The investigator will be invited to participate in the study based on his/her medical specialty, experience conducting clinical research studies and experience in the use of light-based devices for aesthetic indications. Access to potential study subjects and the investigator’s sincere interest in this study along with expressed willingness to cooperate with the study process and requirements will also be considered.

4 STUDY POPULATION

4.1 Study Subject Recruitment and Selection including procedures for randomization

[REDACTED] male or female subjects who desire laser treatment for lentigines on the hand(s) will be studied for each of the laser treatments. Subjects will be recruited to participate from the local population. Subjects may also be recruited from the investigator’s existing patient database or from patients who present themselves to the study site requesting treatment. Only subjects who meet all eligibility criteria and who provide written informed

consent will be enrolled into the study. After verification of eligibility, there will be randomization into one laser group.

4.2 Subject Selection

Each subject will be evaluated by the investigator to assess his/her suitability for entry into the study according to the following inclusion and exclusion criteria.

4.2.1 Inclusion Criteria

To be included in the study, subjects must meet all of the following Inclusion Criteria:

1. Female or Male, 30-90 years of age (inclusive).
2. Fitzpatrick Skin Type I – III.
3. Desires non-invasive and non-ablative treatment of lentigines on the hand(s).
4. Have 4 or more lentigines on the hand(s).
5. Subject must be able to read, understand and sign the Informed Consent Form.
6. Must be willing and able to adhere to the treatment and follow-up schedule and post-treatment care instructions.
7. Willing to have very limited sun exposure and use an approved sunscreen of SPF 50 or higher on the treatment area every day for the duration of the study, including the follow-up period.
8. Willing to have digital photographs taken of the treatment area and agree to use of photographs for presentation, educational or marketing purposes.
9. Agree to not undergo any other procedure(s) for treatment of lentigines during the study, including but not limited to chemical peel, laser and light based device treatment, and home-use device treatment.
10. Agree to not undergo any injection of botulinum toxin, collagen, hyaluronic acid filler or other dermal filler to the treatment area during the study.

4.2.2 Exclusion Criteria

Subjects will be excluded from the study if they meet any of the following Exclusion Criteria:

1. Participation in a clinical trial of another device or drug in the target area within 6 months prior to enrollment or during the study.
2. Any type of prior cosmetic treatment to the target area within 6 months of study participation, such as laser or light-based procedures or surgery.
3. Systemic use of retinoid, such as isotretinoin, within 6 months of study participation.
4. Use of topical medications on the hands, such as antibiotics, benzoyl peroxide, retinoids (isotretinoin), corticosteroids, hydroquinone, or products containing dihydroxyacetone or alpha-hydroxy with concentration > 8%, within 1 month of participation.
5. History of malignant tumors in the target area.
6. Skin abnormalities in the target area, e.g., cuts, scrapes, wounds, scars, large moles.
7. Pregnant.
8. Having an infection, dermatitis, or a rash in the treatment area.

9. History of keloid scarring, hypertrophic scarring or of abnormal wound healing.
10. Any use of medication that is known to increase sensitivity to light according to investigator’s discretion.
11. History of radiation to the treatment area or undergoing systemic chemotherapy for the treatment of cancer.
12. History of pigmentary disorders, particularly tendency for hyper- or hypo-pigmentation.
13. Anytime in life, having have used gold therapy (gold salts) for disorders such as rheumatologic disease or lupus.
14. Excessively tanned in areas to be treated or unable/unlikely to refrain from tanning during the study.
15. In the opinion of the investigator, any physical or mental condition which might make it unsafe for the subject to participate in this study or which requires systematic therapy that could interfere with this research study.

4.3 Subject Discontinuation Criteria

Participation in this study is completely voluntary and a subject can choose to withdraw from the study at any time. In addition, a subject can be discontinued for any of the following reasons: the principal investigator decides that continuing in the study would not be in the subject’s best interest, a subject is noncompliant with the protocol, a subject has a serious reaction to the treatment, or the study is stopped by the study sponsor. In addition, subjects will be discontinued from the study if s/he develops any of the exclusion criteria.

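### Minor: Section 4.3 ends study participation, not only laser treatment, for anyone who develops an exclusion criterion, so an early local skin reaction can cost the 4-week primary count

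*Combined protocol and SAP*

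**What the plan says.** The final sentence of Section 4.3 reads: "In addition, subjects will be discontinued from the study if s/he develops any of the exclusion criteria". The sentence before it lists reasons for which a subject may be discontinued. One of these is that "a subject has a serious reaction to the treatment", and there the wording is permissive.

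Two exclusion criteria in Section 4.2.2 describe conditions that a laser could itself produce:

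- Criterion 6: "Skin abnormalities in the target area, e.g., cuts, scrapes, wounds, scars, large moles".
- Criterion 8: "Having an infection, dermatitis, or a rash in the treatment area".

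Criterion 4 is also relevant, though less directly: "Use of topical medications on the hands, such as antibiotics, benzoyl peroxide, retinoids (isotretinoin), corticosteroids, hydroquinone". It continues with further products and ends with a window of 1 month before participation.

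The primary endpoint (3.1.1) is percent reduction in the number of hand lentigines 4 weeks after the final treatment. Section 3.3.1, whose opening is partly redacted, gives its source: "physician at the study site will be asked to perform an assessment of baseline and 4 weeks post-treatment subject photographs". The later photographs belong to the final follow-up visit (5.3): "Digital photographs of the treated area(s) will be taken". Section 3.4 asks for photographs at baseline and "prior to all laser treatments, immediately after each laser treatment, and at the end of study visit".

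**The concern.** Stopping treatment and stopping follow-up are separate decisions. Section 4.3 joins them. If the sentence is applied as written, whether a subject has a primary outcome can depend on how the skin responded to the laser. The Section 9.2 summaries would then describe subjects without an early local reaction, not everyone treated.

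Section 4.3 also becomes inverted on this reading: a mild rash forces exit, while a serious reaction only permits it.

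Safety information is less exposed. Section 6.2 keeps related adverse events under follow-up and requires a non-completion form when an event ends participation. Section 9.2 reports the proportion who leave early because of a treatment-related event. What may be lost is the efficacy data: the photographs, the count, the global assessment and the questionnaire.

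**Working it through.** **Step 1. Does the rule reach a laser-caused reaction?** On its wording, yes. It covers any exclusion criterion and exempts nothing caused by the study treatment. Criteria 6 and 8 are conditions of the skin at the time of assessment and have no severity grade. Criterion 4 looks back from entry, so the argument that a topical antibiotic or corticosteroid given for a reaction triggers exit is weak. It needs the window to be re-read as applying during the study, and no visible text says such drugs would be used.

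**Step 2. When would the count be lost?** Only if the reaction is found before the final visit. One first seen at that visit costs nothing, because the photographs are taken then. Sections 3.4 and 3.1.1 allow for repeat laser visits, which would be earlier contact points. If a subject is removed at such a visit without being lasered, no visible text requires either a photograph that day or a later 4-week visit.

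**Step 3. How large could the effect be?** The plan has no figure to reproduce: the sample size rests on clinical judgment (9.1), and no reaction rate, SD or dropout rate is given. The following is illustrative.

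Inputs from the documents: up to 12 per arm (Protocol Summary) and up to 24 per arm (Sections 3 and 9.1). The two conflict, so both are used. Assumptions: one or two subjects lost per arm; a gap g of 10 or 30 percentage points in mean reduction between lost and retained subjects, in either direction; SD 20, with 30 as a check.

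- Shift in the completer mean: b = (number lost / arm size) × g. Example, 2 of 12 and g = 30: 0.1667 × 30 = 5.00.
- 95% CI half-width: h = t(0.975, n−1) × SD / √n, with n completers. Example, n = 10 and SD 20: 2.262 × 20 / √10 = 14.31.
- Coverage of the all-treated mean: P(|T| < t(0.975, n−1)), where T is noncentral t on n−1 degrees of freedom with noncentrality b / (SD/√n).

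Results at SD 20, each pair for g = 10 and g = 30:

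| Lost | n | Shift b | h | b/h | Coverage |
|---|---|---|---|---|---|
| 1 of 24 | 23 | 0.42; 1.25 | 8.65 | 5%; 14% | 94.9%; 94.1% |
| 2 of 24 | 22 | 0.83; 2.50 | 8.87 | 9%; 28% | 94.6%; 91.3% |
| 1 of 12 | 11 | 0.83; 2.50 | 13.44 | 6%; 19% | 94.8%; 93.4% |
| 2 of 12 | 10 | 1.67; 5.00 | 14.31 | 12%; 35% | 94.4%; 89.1% |

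At SD 30 the half-widths are 12.97, 13.30, 20.15 and 21.46, and coverage at g = 30 is 94.6%, 93.4%, 94.3% and 92.4%.

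The cost in precision is also small. In SD units the half-width goes from 0.42 (24 subjects) to 0.44 (22), or from 0.64 (12) to 0.72 (10).

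**The case against.** The best counter-argument is that the literal reading cannot be what the authors meant. Criterion 2 excludes cosmetic treatment of the target area, lasers included, within 6 months of participation. Re-applied during the study with no exception, it would remove every subject after the first study laser session. The list was therefore not written with effects of the study laser in mind, and the sentence more plausibly covers intercurrent events such as pregnancy, a new drug or another procedure. Two other places agree: 4.3 deals with treatment reactions in a separate, discretionary clause, and 5.3 expects subjects with previously recorded adverse effects to attend the final visit. This stands as a fair account of probable intent. It does not settle the matter, because no visible words limit the sentence in that way.

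The second argument is redaction. Sections 3.2 and 5.2, most of Section 6 and part of 9.2 are hidden. The number of treatments is unknown, and the 5.2 heading allows for just one. The planned Enlighten schedule, April to June 2016 including a 4-week follow-up, leaves little room for repeat sessions, though that is inference. With one session and no interim visit, none of the contact points identified above would arise. Section 3.4 also requires end-of-study photographs without saying whether that includes early leavers. This stands too, and it is why the point concerns what the rule can do.

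A reader might go further and infer that the plan has no early-exit procedure, or that it inflates efficacy by discarding poor responders. The documents support neither: the first may be in redacted text, and nothing shows whether subjects with a reaction clear more or fewer lentigines.

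**Conclusion.** The point holds as a minor, inexpensive improvement. The visible sentence in 4.3 ends study participation for conditions that the laser may cause, and no visible text keeps the 4-week assessment for those subjects. The case rests on criteria 6 and 8; criterion 4 adds little.

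Frequency and direction are unknown. Under the assumptions shown, the shift stays below the CI half-width in every case, and coverage falls below 91% only with 2 of 12 lost, a 30-point gap and SD 20. The visible analysis is descriptive, with no planned hypothesis test, so no formal conclusion depends on it. The conclusion assumes that the sentence is applied as written, that there is a contact before the final visit, and that no redacted text retains these subjects.

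**What to change.** In 4.3, replace the last sentence with:

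> A subject who develops an exclusion criterion after the first laser treatment (study laser sessions themselves do not count as prior treatment under criterion 2) will receive no further laser treatment, but will be asked to attend the visit 4 weeks after the last treatment received (photographs, lentigo count, global assessment, questionnaire, AE check) unless consent is withdrawn.

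The bracket is confined to the laser session itself, so a wound or infection caused by the laser still stops further laser.

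In 9.2, add that these subjects are summarised in their randomised arm. Also add that any who started a confounding treatment in the target area (for example topical hydroquinone, a retinoid or another device) are listed, so that the summary can also be shown without them. Check both additions against the redacted text for overlap.

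The cost is one sentence in 4.3, a short addition to 9.2, and an already scheduled, non-invasive visit for a few subjects. Stopping the laser remains mandatory, so safety is not loosened. The downside is that a few partly treated or confounded subjects enter the summaries, and efficacy may look slightly lower.
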